6.0 REGISTRATION AND RANDOMIZATION

6.1. Registration:

To register a participant who meets the eligibility criteria and who has signed the informed consent document, study staff will enter the information outlined in section 6.2 in the OnCore database.

6.2. Information Requested at Registration:

- 6.2.1** Firstname
- 6.2.2** Last name
- 6.2.3** eMRN
- 6.2.4** Birth Date
- 6.2.5** Gender
- 6.2.6** Race
- 6.2.7.** Ethnicity

6.3. Initial Assessment:

After consent procedures are completed, the patient, with the help of the study coordinator, will complete a baseline assessment (See section 7).

6.4 Randomization Procedures:

The two intervention arms are as follows:

Arm 1= MAAT-G intervention

Arm 2 = Supportive therapy (time and attention control)

A computer-generated random numbers table, stratified by stage (local [stage I-III] and advanced [stage IV]) with equal probability of block size 2 or 4 will be used to assign participants to one of the two treatment arms. The randomization will assign participants to the two arms in the ratio 1:1. The random numbers tables will be generated centrally using R software. A total enrollment of 85 participants is planned to accommodate for potential 15% attrition, with at least 35 participants in each treatment arm.

Subjects can be registered prior to obtaining baseline measures however, subjects will not be aware of which arm they are randomized to until after the baseline assessment. After registered, they will be scheduled to undergo baseline measures. At the end of the visit for baseline assessment, they will be randomized.

7.0 TREATMENT PROTOCOL

7.1 Measures:

Patient measures will include *demographics, cognitive, psychological, and functional independence* measures. The battery was selected based upon our experience in prior studies.^{1,26,50,51} Based upon experience in prior studies, we estimate the cognitive evaluation will take approximately 60 minutes to complete^{1,3} and the demographics, psychological and functional independence measures will take approximately 20 minutes.

Demographics: Patient and caregiver demographics will be collected, including age, gender, race, ethnicity, marital status, education and socio-economic status will be captured. Cancer and treatment variables, comorbidities, and medications list will be collected from the medical record by study staff.

Cognitive Evaluation will include: 1) FACT-Cog⁵², a validated patient reported outcome measure created to assess cognitive challenges identified by patients with cancer; 2) Brief Test of Adult Cognition by Telephone⁷⁹ (BTACT), a slightly modified version that assesses multiple dimensions central for effective functioning across adulthood; 3) Cambridge Neuropsychological Test Automated Battery (CANTAB) delayed match to sample test⁵³ (DMS), Rapid Visual Information Processing (RVP), and Paired Associates Learning (PAL), validated, computerized tests that assess short- term visual/spatial memory, sustained attention, and visual memory/new learning; 4) Controlled Oral Word Association (COWA)⁵⁴, a measure of verbal fluency evaluating expressive language and executive function; and 5) Hopkins Verbal Learning Test-Revised (HVLT-R)⁵⁵, a validated test of verbal learning and memory. All measures are “paper and pencil”, except for the CANTAB (computer-based assessments that, due to COVID-19, will be administered virtually by collecting patients’ emails and sending a web- based link). COWA, HVLT-R, and BTACT require the study coordinator to administer the tests; they can be administered virtually so study coordinator will schedule a telephone or televideo meeting with the patient at the corresponding time points, as needed.

Psychological Assessment: will include Geriatric Depression Screen (GDS)⁵⁷, Generalized Anxiety and Depression (GAD-7)⁵⁸, and Intolerance of Uncertainty Scale-Short Form (IUS-12). IUS-12 will be administered by the study coordinator over the phone or via televideo (Zoom application) at the appropriate time points.

Functional Independence: IADLs will be measured⁵⁹. IADL will be administered by the study coordinator over the phone or via televideo (Zoom application) at the appropriate time points.

Phase II semi-structured interview questions for patients and caregivers will focus on perceptions of cognitive change and potential benefit of intervention sessions.

7.1 Study Procedures:

Baseline: Following informed consent, patients will undergo Time Point (TP) 1 assessment. Patients will be provided with a data-enabled tablet with HIPAA-compliant video-conferencing application and instructed on its use, participant workbook (for MAAT-G intervention participants only), and tablet instruction manual. The study coordinator will give the patients a drawstring bag to hold all study materials given at TP1. At the time of enrollment, the study coordinator will assign each patient a unique meeting ID number within the tablet instruction manual. This meeting ID number allows each patient to log on to the video-conferencing application and speak to trained clinician (e.g. the MAAT-G Interventionist). Study coordinators will train and support patients on the use of the tablet and video conferencing application. No data is being stored on the tablet itself. If patients consent to have sessions recorded, this will be done through the HIPAA-compliant Zoom software application. If participants do not have access to wireless internet, the tablet will be equipped with a data package for participant use for the purposes of this study. At completion of the study, patients will return the tablet to the study coordinator. If the tablet is lost or stolen during the study, no PHI will be stored on the tablet and thus would not be accessible. If the tablet is broken during the course of the study, we will provide participants with another tablet for use during the study period. The participant would contact the study coordinator with any concerns or problems with using the tablet, contact information will be provided during training on tablet use.

Intervention Period: The intervention period is 10-12 weeks; 10 weekly workshops will be delivered through video-conferencing on the tablet. Workshops will be audio-recorded for fidelity review. (See section 7.2)

Follow-up: Within 1 day to 4 weeks of intervention completion (approximately week 10-14), patients will undergo TP2 assessment.

Patient assessments will be performed by trained study coordinators. As a safety precaution due to COVID-19, patients may take surveys home for completion (e.g. demographics) and then mail back to study team in order to minimize the amount of in-person contact between coordinators and patients; the method of completing surveys at home has been successful in prior studies with good retention.^{43,48} However, to encourage the completion of the surveys, the study coordinator will schedule a telephone or televideo meeting with the patient, as needed, to ensure patients' questions concerning the surveys are addressed. Study coordinators will score assessments and transcribe results into a database. Audio- recordings will be deleted following transcription.

Semi-structured interviews will be conducted by a trained study coordinator who is not responsible for any other component of the study. Interviews will be conducted with patients and if consented, will include caregivers. As a safety precaution due to COVID-19, the interviews with the patients and caregivers will be conducted over the phone or over Zoom televideoconferencing application. These audio-recorded interviews will be conducted after completion of the intervention.

Location: Participation in workshops will take place through video-conferencing. Participants will be encouraged to participate from their home or other private location. Due to COVID-19, the Department of Psychology is conducting clinical visits from their clinical office and home office locations until further notice. Wherever the location may be, the trained clinician (e.g. psychologist psychology post-doctoral

fellow, psychology intern, or Research Registered Nurse [RN] trained in MAAT-G) who is conducting the interventions will ensure privacy in a private room with a closed door. Participants will be provided with a HIPAA compliant tablet to use for participation in the intervention activities and the intervention will be delivered using HIPAA compliant video-conferencing technology provided by the University of Rochester. The coordinator will be in touch with patients by phone throughout the length of the study, serving as a liaison between patient and trained clinician MAAT-G Interventionist. Coordinator will help organize the scheduling/rescheduling of workshop sessions and will be available for any patient questions.

7.2. Study Interventions

7.2a. MAAT-G Intervention

The MAAT-G intervention will be delivered by a trained clinician (also described as MAAT-G Interventionist and includes psychologist, psychology post-doctoral fellow, psychology intern, or Research RN trained in MAAT-G) at the University of Rochester Medical Center. The intervention will be delivered through televideoconferencing and participants will be provided a tablet equipped with a HIPAA compliant televideoconferencing application to use for the MAAT-G workshop sessions. We will use the University of Rochester Zoom application which is HIPAA compliant. A tablet instruction manual will be given to patients to help guide them through how to use a tablet and how to navigate the Zoom application. A unique meeting ID number will be given to each patient to log in to the Zoom application. If participants do not have access to wireless internet, the tablet will be equipped with a data package for participant use for the purposes of this study.

Participants will also be provided a workbook for skills practice in between workshop sessions. A summary of workshop content is provided in table 2 below.

During Workshop #2, the study coordinator or trained MAAT-G Interventionist will provide patients a link to a Vimeo video. The coordinator will email the link to patients a couple days before Workshop #2. The Vimeo video has been created by the study team and talks patients through how to remain relaxed before stressful events occur. Study patients will be able to access the video without providing any personal information to the website.

Table 2: MAAT-G workshop content WORKSHOP VISIT:	Content/Strategies:
1	
• Introduction to MAAT• Self-Awareness and monitoring of memoryproblems
2	
• Progressive Muscle Relaxation• Quick Relaxation
3	
• Self-Instructional Training• Verbal and silent rehearsals
4	1. Cognitive restructuring
5	2. Keeping a schedule 
• Memory routines
6	1. External cueing 
• Distraction reduction
7	1. Activity scheduling and pacing 2. Active listening

8	1. Fatigue management 2. Sleep improvement
9	
 • Visualization strategies
10	
 • Tying it all together

7.2b. Supportive care control condition

Supportive Therapy (ST) is a “behavioral placebo” and controls for non-specific psychotherapeutic factors of the clinician-subject relationship, such as empathy and support, but does not provide active cognitive training. ST utilizes reflective listening to help deepen awareness of participants’ emotional experience. ST was used as the control condition for a prior MAAT study.⁷¹ A clinician manual for ST has been developed.⁷¹ Timing and duration of ST sessions will mirror the intervention, and will consist of 10 weekly sessions, 30 to 45 minutes each, delivered by a trained clinician (e.g. psychologist, psychology post-doctoral fellow, psychology intern, or Research RN) via video-conferencing.

We will offer subjects who are randomized to the Supportive Therapy (ST) group the opportunity to receive the MAAT-G Intervention after their completion of the 10 ST sessions and the post-intervention follow-up time point procedures. We will not administer an additional evaluation during this time period if patients elect to proceed with MAAT-G after completing study procedures (e.g. no further time points for followup of cognition or survey measures). If patients do elect to continue with this, we will continue to monitor for potential adverse events that are related to the behavioral intervention (see Data Safety Monitoring section below). Participants electing to continue and receive MAAT-G after completing study procedures can discontinue at any time. If subjects decide to get the MAAT-G intervention, they do not need to complete all 10 sessions or within a certain timeframe. We will collect data on the number of ST subjects who chose to do the additional MAAT-G Intervention and the number of sessions completed. The intent of allowing patients randomized to ST to continue and receive MAAT-G after completion of study procedures is to facilitate retention.

The University Advarra system will be used per WCI policy for study reimbursement for \$30 per time point/workshop. The templated RSRB information for Advarra will be used for information for patients for use of the gift card system. The study team will collect W-9 to sent to University Accounts Processing for study payment documentation and send to [contact]. Following this, the participant W-9 will be shredded. W-9 information will not be kept by the study team.

7.3. Potential risks:

A participant may become more aware of any attention or memory problem they are experiencing as a result of participation in this study, potentially increasing psychological stress. While this is unlikely to provoke significant problems, the PI ([name]) will be available for evaluation and referral to appropriate behavioral care if needed.

Risks to privacy using telehealth and telecommunications are a potential concern. We also recognize that while encryption of videoconferencing makes breeches of private information unlikely, not all risks to privacy can be completely eliminated. We will inform all participants using the telehealth equipment of this.

7.4. Potential benefits:

There may be no direct benefits to participation in this study. However, the study will provide useful information about systemic cancer therapy-associated cognitive problems for older adults and strategies for helping patients cope with memory and attention problems.

8.0 DATA MANAGEMENT

8.1. Data Handling and Statistical Considerations:

8.1.1. The same protocols and procedures for data quality and control that are readily used for prior studies conducted with the Geriatric Oncology Research Group and currently being overseen by our office. Data will be entered into REDCap (see section 8.3.5 below).

8.1.2. After entering into REDCap, data are audited visually for errors. R, SPSS and SAS will be used for the statistical analyses. Unless otherwise stated, all statistical tests will be performed at the two-tailed 5% level of significance. Likewise, 95% confidence intervals will be constructed for the estimation of effects.

8.1.3. The assumptions underlying all statistical analyses will be thoroughly checked using appropriate graphical and numerical methods.^{65,66} In case of violations of distribution assumptions such as normality, appropriate nonparametric methods will be attempted.^{67,68} If outliers or influential data are detected, the accuracy of the data will be investigated. If no errors are found, analyses may be repeated after removing these cases to evaluate their impact on the results. However, the final analyses will include these data points.

[figure not shown]
8 . 2 . Data Analysis and Sample Size:

Data Analytic Plan:

Power Analysis and Sample Size Consideration: The effect size for MAAT-G concurrent with systemic cancer therapy in older adults is not known; the purpose of this study is to gather preliminary efficacy data on perceived cognition (FACT-Cog). MAAT has demonstrated a medium effect size ($d = 0.52$) on FACT-Cog in younger cancer survivors. Using analysis of covariance (ANCOVA) design and pre-post correlation of 0.5, a sample size of $n=35$ evaluable patients per group will provide 80% power to detect an effect size of 0.52 at the significance level of 0.10 (**Figure 1**). Assuming 15% attrition, we will enroll 85 patients.

Quantitative Data Analysis: Underlying assumptions to all statistical analyses will be checked using appropriate graphical and numerical methods.⁷² In the case of serious violation of assumptions, appropriate transformations or nonparametric methods will be used.^{73,74} If outlying observations are encountered, data will be checked. If no errors are found, we will conduct analyses with and without the outlying data and compare results. Bivariate associations between treatment group and participant variables (demographics, cancer and treatment characteristics, baseline assessment of outcome measures) will be examined to assess possible imbalance between arms. Since this is a pilot study, will use significance level=0.10 to avoid false negative results, and decrease the risk of abandoning a promising intervention.^{75,76}

Analysis of the primary outcome: To assess the impact of the intervention on patient-reported cognition (FACT-Cog), we will employ the analysis of covariance (ANCOVA). The model will consist of post-FACT-Cog as the outcome and include the arm as the main effect and pre-FACT-Cog as a covariate. We will evaluate the interaction between pre-FACT-cog and the arm. We will adjust for baseline covariates in case that imbalance between arms was detected, and baseline and change in psychological measure (GDS and GAD-7). All non-significant covariates will be removed from the model.

Analysis of secondary and exploratory outcomes: The effect of MAAT-G on objective cognition (CVLT-R, TBANS, CANTAB, COWA, HVLT-R, TMT A/B), functional independence (IADL) and stress response (cortisol) will be assessed with the same strategy as for the primary outcome.

As above, a sample size of 85 patients is planned based upon anticipated attrition rates. If attrition of patients occurs at a higher proportion than anticipated during the trial conduct, we will conduct an interim data analysis check to assess for need in adjusting sample size.

Phase II Qualitative Data Analysis: Semi-structured interviews will be prepared and coded similar to Phase Ib. Potential themes from Phase II interviews include experiences of cognitive failure and perceived timing and mode of onset of symptoms, changes in functional independence, perception of how the intervention (either MAAT-G or ST) influenced symptoms and experience, and experiences with the adaptive behavioral or compensatory techniques used.

Mixed Methods Integration: Qualitative and quantitative data will be integrated (**Table 3**) to enhance our understanding of the participant experience with MAAT-G and explore potential benefits beyond what is captured in quantitative tools. Our primary outcome, FACT-Cog, is a validated tool to measure perceived cognition and was developed through qualitative methods. However, the average age of patients involved was 59.6 years old,⁷⁷ and it is possible the FACT-Cog does not capture cognitive experiences that are unique to older adults. Quantitative data will be analyzed first to determine longitudinal change in perceived cognition, and then integrated with qualitative data to evaluate if qualitative themes differ between patients who experience longitudinal improvement in perceived cognition versus those with longitudinal decline as well as difference in themes between study arms. Data will be organized using MAXQDA joint displays.⁷⁸

Table 3: Integration plan:

Aim Phase II	Data Collection Procedures	Analysis Procedures	Point of Integration	Example of Integration Enhancing the Detection of MAAT-G Benefits
Estimate the effect of MAAT on FACT-Cog, objective measures of cognition and functional independence and explore through semi-structured qualitative interviews, the patient and caregiver experience with MAAT-G and perception of how MAAT-G influences daily functioning and perceived benefits.	
 Cognitive Assessment (Quant): Perceived: FACT-Cog Objective: Neuro-psychological assessment battery Functional Independence (Quant): IADL Semi-structured interviews (Qual) 	
 Descriptive statistics, t-tests, chi-square tests, logistic regression Theme analysis guided by Phenomenology 	
Merging: Qual and Quant are brought together for analysis
 
Purpose: To use qual data to help explain the quant outcomes; to understand in more depth how the conceptual model mechanism worked; to assess the context when comparisons of outcomes are made with baseline data.
	We will compare themes between patients who report longitudinal improvement in perceived cognition versus those who report longitudinal decline and we will compare themes between study arms. (e.g. patients with longitudinal improvement in perceived cognition or those receiving MAAT-G may report a greater ability to manage the complex schedule of cancer treatments or a greater ability to participate in social roles such as caregiving for a spouse or volunteer activities).

8.3. Records to be Kept:

8.3.1. Data Collection Table:

FORM	SCHEDULE OF DATA COLLECTION	
	Baseline	Post-Intervention
On Study Data (Patient and caregiver demographic information and clinical data)	X	
FACT-COG	X	X
CANTAB	X	X
BTACT	X	X
COWA	X	X
HVLT-R	X	X
	X	X
GAD-7	X	X
IADL Survey	X	X
TUS-1Z	X	X

8.3.2 All hardcopy research records will be stored onsite in the University of Rochester Medical Center, in locked research files at the James P. Wilmot Cancer Center. The Cancer Center is secured with electronic key cards. Offices within the Cancer Center are again secured by key and data is kept in locked file cabinets. Electronic research records are stored on the University of Rochester Medical Center's password secured and firewall protected networks. These are the same methods of security used for patient medical records. All study data will be kept for a period of 10 years after the study and all reports and publications are complete.

8.3.3 All recorded data, such as the audio-recorded interviews/transcripts and Zoom workshop sessions, will be stored on the UR Box drive to assess fidelity of intervention delivery. Within the Box drive, data will be stored in a password protected folder with access restricted to the PI and a subset of study team members. All personal identifiers will be deleted (e.g. de-identified) from the transcriptions of the audio-recordings. Once data is uploaded to the secure server, the data will be deleted from the audio recorders.

8.3.4. All data collected for the current study will be used in post hoc analyses as appropriate. Data will not be used for future studies without prior consent of the patient. The patient's individual research record will not be shared with their treating physician, unless they provide consent or the patient's treating physician is a study physician, in which case they will have access to study data as a study co-investigator. Overall study results will be presented to participants, faculty and staff at the University of Rochester Medical Center after completion of the study. Study results will be presented at professional meetings and published.

8.3.5. The study coordinator will assign a numerical study ID to each participant once they have signed the consent form. All study forms and questionnaires will use this number and the participant's first, middle, and last initials as identifiers, to ensure data integrity. Other identifying information will not exist on these forms. A complete list of study participants with study ID, name, and contact information will be maintained separately. This linkage information will only be accessible to the study coordinator, study investigators, and the individuals responsible for maintaining the database.

8.3.6. Additionally, the data can be collected and managed by the research teams at University of Rochester Medical Center using REDCap¹⁶⁷ electronic data capture tools hosted at URMC.

8.3.6a. URMC provides the following information on the REDCap program: "Vanderbilt University, in collaboration with a consortium of institutional partners, has developed a software toolset and workflow methodology for electronic collection and management of research and clinical trial data, called REDCap (Research Electronic Data Capture). The REDCap system is a secure, web-based application that is flexible enough to be used for a variety of types of research. It provides an intuitive interface for users to enter data and real time validation rules (with automated data type and range checks) at the time of data entry. REDCap offers easy data manipulation with audit trails and functionality for reporting, monitoring and querying patient records, as well as an automated export mechanism to common statistical packages (SPSS, SAS, Stata, R/S-Plus). Through the REDCap Consortium, Vanderbilt has disseminated REDCap for use around the world.

Currently, over 240 academic and non-profit consortium partners on six continents with over 26,000 research end-users use REDCap”¹⁶⁸.

8.3.56. According to the Clinical and Translational Science Institute (CTSI), REDCap is supported with the following means. “The *CTSI Informatics Core*, a unit of the SMD *Academic Information Technology (AIT) Group*, will serve as a central facilitator for data processing and management. REDCap data collection projects rely on a thorough study-specific data dictionary defined in an iterative self-documenting process by all members of the research team, with planning assistance from the *AIT-CTSI Informatics Core*. The iterative development and testing process results in a well-planned data collection strategy for individual studies”¹⁶⁸.

8.3.6c. The CTSI states that regarding security, “REDCap servers are housed in a local data center at the University of Rochester and all web-based information transmission is encrypted. REDCap was developed in a manner consistent with HIPAA security requirements and is recommended to University of Rochester researchers by the URMC Research Privacy Officer and Office for Human Subject Protection.”¹⁶⁸

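### Stage is the only stratification factor, yet the primary ANCOVA omits it and the imbalance check would almost never bring it in; if stage is prognostic, the test is slightly conservative

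*Combined protocol and SAP*

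**What the plan says.** Section 6.4 assigns patients 1:1 from lists "stratified by stage (local [stage I-III] and advanced [stage IV" and uses blocks of 2 or 4. No other stratification factor is named.

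Section 8.2, on the primary outcome, states: "The model will consist of post-FACT-Cog as the outcome and include the arm as the main effect and pre-FACT-Cog as a covariate". It then evaluates the arm by pre-FACT-Cog interaction and adds baseline and change in GDS and GAD-7. Other covariates enter conditionally: "We will adjust for baseline covariates in case that imbalance between arms was detected". The last step is: "All non-significant covariates will be removed from the model". No analysis model names stage.

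The imbalance check is described under Quantitative Data Analysis in the same section. Associations between arm and participant variables, including cancer characteristics, "will be examined to assess possible imbalance between arms". No criterion for imbalance is given. The next sentence says the study "will use significance level=0.10 to avoid false negative results". The effects on the secondary and exploratory outcomes "will be assessed with the same strategy as for the primary outcome".

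**The concern.** Stratifying by stage removes most of the chance difference between arms that stage would otherwise cause. An ANCOVA without stage still counts the variation due to stage in its error term. If stage predicts post-FACT-Cog beyond baseline, the model-based standard error is too large, the interval too wide, and the test runs below its nominal level. Section 8.2 chooses the 0.10 level to reduce the risk of abandoning a promising intervention, and a conservative test works against that aim.

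The conditional route does not repair this, because a balance check is least likely to select the factor that the design has balanced. If dropout differs by stage and arm, omitting stage can also add a small bias that the check would rarely catch.

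**Working it through.** **1. The plan's own figure.** Inputs from section 8.2: 35 evaluable per arm, d = 0.52, pre-post correlation 0.5, significance level 0.10. Tests are two-tailed (8.1.2).

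- Residual variance = 1 − 0.5² = 0.75.
- Standard error = √(2 × 0.75/35) = 0.207, so the noncentrality is 0.52/0.207 = 2.51.
- With 70 − 3 = 67 df the critical value is 1.668, and noncentral-t power is 80.0%, as stated.
- Enrolment: 70/0.85 = 82.4, so 83, within two of the plan: "Assuming 15% attrition, we will enroll 85 patients".

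**2. Can stage enter through the imbalance check?** With blocks of at most 4, the arms differ by at most 2 patients within a stratum. Among all 85 randomised, the smallest reachable chi-square p-value for arm by stage is about 0.16 (only two stage IV patients, both in one arm). A 0.10 screen therefore cannot select stage there, and simulation gave 0 of 360,000 runs. Among evaluable patients (40,000 runs per cell; stage IV shares assumed):

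| Stage IV share | 15% random attrition | 40% dropout for stage IV in one arm, 15% elsewhere |
|---|---|---|
| 10% | 0.28% | 2.5% |
| 20% | 0.07% | 2.7% |
| 30% | 0.02% | 3.1% |

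Fisher's exact test admits stage less often still (0.02% or less, and 0.4-1.7%).

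**3. Effect of omitting stage under random attrition.** Let R² be the share of the variance left after baseline that stage explains. The documents do not give it, so 2%, 5% and 10% are assumed. The total stays at the plan's 0.75.

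- Standard error ratio = 1/√(1 − R²).
- Actual level = 2·P(T₆₇ > 1.668/√(1 − R²)).
- Power: noncentral t with true residual variance 0.75(1 − R²), on 67 df without stage and 66 with it.

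At R² = 5%, the true residual variance is 0.7125 and the ratio is 1/√0.95 = 1.026. The effective cutoff is 1.668 × 1.026 = 1.711, which gives an actual level of 9.2%. The noncentrality is 0.52/√(2 × 0.7125/35) = 2.577. Power is 80.6% at the 1.711 cutoff, and 81.7% with stage in the model (cutoff 1.668).

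| R² | SE overstated by | Actual level | Power without stage | Power with stage | Points forgone |
|---|---|---|---|---|---|
| 2% | 1.0% | 9.7% | 80.2% | 80.7% | 0.5 |
| 5% | 2.6% | 9.2% | 80.6% | 81.7% | 1.2 |
| 10% | 5.4% | 8.3% | 81.2% | 83.5% | 2.3 |

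Differences are taken before rounding.

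The stage effect given baseline that each row needs is √(0.75·R²/(p(1 − p))) for stage IV share p. At R² = 10% this is √(0.075/0.16) = 0.68 SD for p = 20%, or √(0.075/0.09) = 0.91 SD for p = 10%. These are large effects, so the first two rows are more plausible.

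**4. Allowing for mood adjustment.** If half of stage's share runs through GDS and GAD-7, R² falls to 1%, 2.5% or 5%. The standard error is then overstated by 0.5%, 1.3% or 2.6%, and 0.2, 0.6 or 1.2 points are forgone.

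**5. Sensitivity to how stage variance is counted.** If the stage effect is added on top of 0.75, simulated power without and with stage is:

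- 79% and 81% for 20% stage IV and a 0.5 SD effect;
- 77% and 81% for 30% and 0.8 SD;
- 74% and 81% for 30% and 1.0 SD.

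With stage in the model, the type I error was 0.098-0.103 in every scenario.

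**6. Differential dropout.** Assume 40% dropout for stage IV in one arm and 15% elsewhere. The difference between arms in stage IV share among evaluable patients is p − 0.60p/(0.60p + 0.85(1 − p)). For p = 20% this is 0.20 − 0.12/0.80 = 0.05; for 10% and 30% it is 0.027 and 0.068. Bias is this difference times the stage effect. At R² = 5% and p = 20%, it is 0.05 × √(0.0375/0.16) = 0.05 × 0.484 = 0.024 SD. Over p = 10-30%, the bias is 0.011-0.018, 0.018-0.029 or 0.025-0.041 SD for R² of 2%, 5% or 10%. Simulation at R² = 5% gave 0.019-0.033 SD without stage and within 0.006 of zero with it. With 25% dropout in place of 40% and R² of 5%, the bias is 0.007-0.011 SD.

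**The case against.** The strongest objection is that section 8.2 never states the imbalance criterion. The 0.10 sentence gives a reason that belongs to the efficacy test, so reading it as the screening level is an inference. A rule based on standardised differences would admit stage far more often under random attrition: 31-39% of trials at a cutoff of 0.1 and 5-9% at 0.2. Under the 40% dropout scenario the rates are 59-69% and 27-36%. It is true that the entry rates depend on a significance screen. However, significance levels are the only thresholds the plan states, the 5% default in 8.1.2 would admit stage even less often, and no standardised-difference rule appears. The removal rule could also drop stage after entry.

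Second, the plan does not stop at arm plus pre-FACT-Cog, so conservatism has not been shown for the model left after GDS and GAD-7 adjustment and covariate removal. That limit stands.

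Third, the consequence is small for a pilot, and the 40% dropout figure is constructed: in a trial of 85 it means roughly one to three extra patients lost. For comparison, section 3.6c reports 89% completion at three months in a related pilot. This is fair, and it is why the point is minor. It does not argue against a correction that costs almost nothing.

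**Conclusion.** The concern holds, as a minor gap in pre-specification and efficiency. In effect, the plan analyses without its own design factor. For the arm + pre-FACT-Cog model under random attrition, the more plausible loss is 0.5-1.2 points of power and an actual level of 9.7-9.2% against a nominal 10%. There is no bias and no type I error inflation, and the planned 80% power is met when the residual variance is the plan's own 0.75. If a large stage effect came on top of that variance, the loss would be greater (step 5). Bias under the assumed differential dropout is at most 0.041 SD, against a target effect of 0.52.

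The stage IV share, the prognostic strength of stage and the dropout pattern are assumptions, since the documents give none of them. If stage adds nothing beyond baseline, nothing is lost. No assurance is given for the model after GDS/GAD-7 adjustment and covariate removal.

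**What to change.** State in section 8.2 that the primary ANCOVA contains arm, pre-FACT-Cog and stage (I-III versus IV). Stage should be a fixed covariate, exempt from both the imbalance-based entry rule and the removal of non-significant covariates. Apply the same to the secondary ANCOVAs.

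The cost is one sentence and one degree of freedom: if stage has no effect, power goes from 80.00% to 79.99%. Stage is already known at randomisation, so no new data are needed, and the sample size does not change.
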